6.2 Study Duration and Visit Schedule

The CTN-0067 CHOICES scale-up study will target enrolling 350 participants over approximately 22 months at no more than 8 HIV clinic sites. Each participant will be engaged in the overall study for an expected duration of 25-28 weeks (**Figure 3**) as follows:

- Weeks 1-4: consent, screening, randomization.
- 24 weeks: Active treatment with study visits every 4 weeks.
- Week 24: A single follow-up visit at the end of active treatment.

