15.0 SAFETY ASSESSMENTS

15.1 Adverse Events, including Serious Adverse Events, and Protocol Deviations

Adverse Events, Serious Adverse Events, and Protocol Deviations will be assessed and documented.

Study staff members will assess for any medical or psychiatric side effects by asking: "How have you been feeling since your last visit?" AEs will be solicited at each study visit but will be recorded at any visit after consent when reported by the participant according to the adverse event reporting definitions and procedures outlined in the protocol.

If a reported AE suggests medical or psychological deterioration, it will be brought to the attention of the study clinician for further evaluation. SAEs will be medically managed, reported, and followed in accordance with applicable regulatory requirements. Safety assessments will be performed at all visits.

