17.13 Safety Analysis

Adverse events (AEs), including serious adverse events (SAEs), will be summarized by body system and preferred term using MedDRA (The Medical Dictionary for Regulatory Activities). Adverse events will be presented in two ways: (1) the number and proportion of participants experiencing at least one incidence of each event will be presented overall and by treatment group; and (2) a table displaying the total number of each event will be given overall and by treatment group. Listings of serious adverse events will be given, sorted by treatment, body system, and preferred term. Detail in these listings will include severity, relationship to study drug, and action taken as available. Treatment arm differences will be monitored by the DSMB.

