23.9 Participant Withdrawal

The study medical clinician must apply his/her clinical judgment to determine whether or not an adverse event is of sufficient severity to require that the participant is withdrawn from further study medication administration. Extended-release naltrexone will be discontinued in participants with evidence of clinically significant deterioration in hepatic function and/or acute hepatitis, as assessed by the study clinician. The study medical clinician should consult with the site principal investigator, the lead investigator and/or Medical Monitor as needed. If necessary, a study medical clinician may suspend any trial treatments and institute the necessary medical therapy to protect a participant from any immediate danger. A participant may also voluntarily withdraw from treatment due to what he/she perceives as an intolerable adverse event or for any other reason. If voluntary withdrawal is requested, or the participant has been removed from the study, the participant will be asked to complete an end of study visit to assure safety and to document end of treatment outcomes and will be given recommendations for medical care and/or referrals to treatment, as necessary.

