24.2.5.3 Human Subject Protection

The study medical clinician will evaluate all pertinent screening and baseline assessments prior to participant randomization to ensure that the participant is eligible and safe to enter the study. Adverse events (AEs) and concomitant medications will be assessed and documented at each clinic visit. Individuals who experience an AE that compromises safe participation will be discontinued from further medication administration and provided referrals for other treatment or to specialized care. Study personnel will request that the participant complete an end of study visit to assure safety and to document end of treatment outcomes.

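### Section 17.13 shows adverse events by arm with no follow-up time; if observation differs between arms, the arm observed for less time can look safer

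*Combined protocol and SAP*

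**What the plan says.** Section 17.13 plans two AE displays. In the first, "the number and proportion of participants experiencing at least one incidence of each event will be presented overall and by treatment group". For the second, "a table displaying the total number of each event will be given overall and by treatment group". SAE listings accompany them. The section names no denominator for the proportions and plans no test or model, but it adds: "Treatment arm differences will be monitored by the DSMB". No section gives person-time, an incidence rate or a time-to-event summary for AEs.

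On capture, Section 15.1 states: "AEs will be solicited at each study visit but will be recorded at any visit after consent when reported by the participant". Section 6.2 sets the schedule: "24 weeks: Active treatment with study visits every 4 weeks". The trial is unblinded (Section 9.7), with 175 participants planned per arm (Section 17.1).

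On how long participants stay under observation, the sections do not agree:

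- Section 9.6 follows everyone to the end unless consent is withdrawn or the investigator or sponsor ends enrollment.
- Section 12.8 separates stopping treatment from stopping the trial. Section 12.9 explains being finished with the study as death or withdrawal of consent.
- Section 24.2.5.4 (Pregnancy) expects people who come off medication to keep attending.
- Section 24.2.5.3 reads differently: "Individuals who experience an AE that compromises safe participation will be discontinued from further medication administration". It then asks them for an end of study visit.
- Section 23.9 says that after voluntary withdrawal, or removal from the study, "the participant will be asked to complete an end of study visit to assure safety and to document end of treatment outcomes". Whether the withdrawal meant is from treatment or from the study is unclear.
- AE collection runs to 30 days beyond the final study visit in Section 23.4, but to 30 days beyond the final active treatment visit in Section 24.2.1.

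**The concern.** Someone no longer seen has fewer chances to report an event. A crude proportion or count therefore combines two things: how often events happen and how long people were watched. If one arm is watched for less time, its crude figures fall even when the underlying rates are the same. In an open-label comparison with a four-weekly visit schedule, equal observation should be shown rather than assumed.

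At stake is how the DSMB and later readers interpret the harms of XR-NTX against usual care. If XR-NTX participants leave earlier, XR-NTX harms are understated; if usual-care participants leave earlier, they are overstated. The tables as planned would not reveal which had happened, or whether either had.

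**Working it through.** The plan states no AE rate, exit rate or safety precision, so there is no planned figure to reproduce. What follows is an illustration.

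**Inputs from the documents:** 24 weeks of planned follow-up (Section 6.2); 175 per arm (Section 17.1).

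**Assumed inputs:** the same constant weekly rate L in both arms; a share f of an arm exits at week 8; exit is unrelated to AEs.

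**Formulas**

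- Mean follow-up = 24(1 − f) + 8f weeks.
- Expected events = 175 × L × mean follow-up.
- Proportion with at least one event = (1 − f)(1 − e^(−24L)) + f(1 − e^(−8L)).

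**Main case: L = 0.05, f = 20% versus 5%**

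- Mean follow-up: 0.80 × 24 + 0.20 × 8 = 20.8 weeks, versus 0.95 × 24 + 0.05 × 8 = 23.2 weeks.
- Count ratio: 20.8 / 23.2 = 0.90.
- Proportions: 1 − e^(−1.2) = 0.6988 and 1 − e^(−0.4) = 0.3297. This gives 0.80 × 0.6988 + 0.20 × 0.3297 = 62.5%, versus 0.95 × 0.6988 + 0.05 × 0.3297 = 68.0%, a gap of 5.5 points.

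**Other cases**

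| L per week | Exits at week 8 | Proportions | Gap (points) | Count ratio |
|---|---|---|---|---|
| 0.02 | 20% v 5% | 33.5% v 37.0% | 3.5 | 0.90 |
| 0.05 | 30% v 10% | 58.8% v 66.2% | 7.4 | 19.2 / 22.4 = 0.86 |
| 0.05 | 15% v 10% | 64.3% v 66.2% | 1.8 (unrounded) | 21.6 / 22.4 = 0.96 |
| any | equal shares and timing | equal | 0 | 1.00 |

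Over a wider set of assumptions (0.1 to 2 events per 24 weeks, exits of 10% versus 20 to 40%, at week 8 or 12), the ratio of proportions runs from 0.79 to 0.97 and the ratio of counts from 0.79 to 0.95.

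**With follow-up time added, main case**

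- Person-weeks: 175 × 20.8 = 3,640 and 175 × 23.2 = 4,060.
- Expected events: 0.05 × 3,640 = 182 and 0.05 × 4,060 = 203.
- Rate: 5.0 per 100 person-weeks in both arms, ratio 1.00.
- Cumulative proportion with a first event by week 24, censoring at exit: 69.9% in both arms.

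**Where the illustration does not apply**

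- *Exit caused by a first AE.* That event is already counted, so the proportion with any AE does not fall. Only later events are lost from the counts.
- *Events confined to the first 8 weeks.* Exit at week 8 loses nothing and the crude displays agree. Events per person-week would then be 4,060 / 3,640 = 1.12 times higher in the arm with more exits, which is misleading in the other direction. The cumulative first-event display stays equal.

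**The case against.** The strongest objection is that nothing in the documents shows that follow-up will be unequal. A reader might infer that people who stop medication are taken out of the study, that this falls mainly on XR-NTX because usual care has no study-supplied drug, and that XR-NTX harms will therefore be understated. The documents do not support that chain. Sections 9.6, 12.8, 12.9 and 24.2.5.4 keep people in follow-up after treatment stops. Section 23.9 applies only after voluntary withdrawal or removal. Only Section 24.2.5.3 clearly reads as exit after a medication stop, and there the AE that led to the stop has already been recorded. This objection stands: unequal exit is a possibility, not a prediction.

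The direction is open for other reasons too. Injection-site examination (Section 13.7) and recording of precipitated withdrawal (Section 15.4) apply only to XR-NTX and can raise its ascertainment. Person-time does not correct that. Detoxification and induction fall in weeks 0 to 4 (Section 9.2.3.1), so the constant-rate assumption is doubtful for harms of that period. Capture is also not wholly tied to visits: Section 15.3 uses chart review and locator contacts for fatal overdose, and Section 9.1.6 allows record abstraction up to 52 weeks after randomization.

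Finally, the tables are descriptive. At 175 per arm and about 65% incidence, the 95% half-width for a difference is 1.96 × √(2 × 0.65 × 0.35 / 175) = 10 points, larger than any gap shown above. That is fair as to size. It does not remove the point, because a shift from unequal observation is systematic, and the plan gives the DSMB no means of seeing it.

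**Conclusion.** The point holds as a conditional one. Section 17.13 omits follow-up time. If the arms are observed for different lengths of time, the less-observed arm can look safer. Under the assumptions stated, the distortion is about 2 to 7 percentage points in the proportion with an event at 0.05 per week, and a count ratio of 0.86 to 0.96. With equal follow-up it is zero. All exit shares, exit times and event rates are assumptions; the documents give none.

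Two stronger readings should be resisted. The documents do not show that XR-NTX harms will be understated, since neither unequal exit nor its direction is established. Nor is any safety test invalid, since none is planned. The risk is that descriptive tables are misread. Severity is low, and the change is worth making because it is cheap.

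**What to change.** Keep both crude tables and state the denominator of the first. In Section 17.13 add, by arm:

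1. Person-weeks of AE observation, from randomization to last AE assessment.
2. Events per 100 person-weeks, beside the count table.
3. The cumulative proportion with a first event by week 24, censored at last AE assessment, beside the proportion table.
4. Study exits by reason.

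Apply items 2 and 3 to any AE, any SAE and the main harms. Read the first-event display alongside the rates, because induction harms may cluster early. Add a note that person-time does not correct for assessments made only in the XR-NTX arm, and that censoring assumes exit is unrelated to the event being analyzed.

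Reconcile Section 24.2.5.3, and the ambiguous Section 23.9, with Sections 9.6, 12.8, 12.9 and 24.2.5.4 on follow-up after medication stops. Reconcile Section 23.4 with Section 24.2.1 on the AE window, since the last AE assessment cannot be defined until one window is stated.

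The cost is a little more programming and longer safety tables. AE assessment is already scheduled at visits (Section 10.1) and a Study Completion form exists (Section 12.9), so no new data collection should be needed.

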18.0 REGULATORY COMPLIANCE AND SAFETY

18.1 Regulatory Compliance

This study will use a commercial IRB as the central IRB of record. Sites will be expected to execute an IRB Authorization Agreement between their local IRB and the central IRB. For sites whose IRBs will not rely on the central IRB, procedures will be developed on a case-by-case basis.

Prior to local study initiation, site investigators will obtain written IRB approval (in most cases this will consist of an IRB Authorization Agreement) to conduct the study at their respective sites. When changes to the study protocol become necessary, amendments will be submitted to the central IRB in writing by the investigators for IRB approval prior to implementation. Annual reports will be submitted to local IRBs as required by local guidelines. Each site investigator is responsible for maintaining research files that include copies of IRB-approved consent documents and all IRB/IEC (Institutional Ethics Committee) approval memos for Initial and Continuing/Annual Reviews, protocol modifications, and any other modification made in the course of the study. All initial approval documents (approval memos and informed consents) must be provided to the Lead Node investigative team prior to the initiation of research activities at a given site and all regulatory documents must be available at any time for an audit.

The study will be registered in www.ClinicalTrials.gov.

18.2 Statement of Compliance

This trial will be conducted in compliance with the current version of the protocol, current Good Clinical Practice (GCP), the principles of the Declaration of Helsinki, and all other applicable regulatory requirements. Participating sites must obtain written approval of the study protocol, informed consent forms, other supporting documents, and any advertising for participant recruitment from their local institutional review board (IRB) in order to participate in the study. This approval is expected to consist of an IRB Authorization Agreement between the local IRB and the central IRB. Prior to study initiation, the protocol and the informed consent documents will be reviewed and approved by an appropriate Ethics Review Committee (ERC) or IRB. Any amendments to the protocol or consent materials must be approved by the central IRB before they are implemented. Annual progress reports and local Serious Adverse Event (SAE) reports will be submitted to each IRB, according to its usual procedures for studies operating under an IRB Authorization Agreement.

18.3 Confidentiality

By signing the protocol signature page, the investigator affirms that information furnished to the investigator by NIDA will be maintained in confidence and such information will be divulged to the IRB, Ethics Review Committee, or similar expert committee; affiliated institution; and employees only under an appropriate understanding of confidentiality with that board or committee, affiliated institution and employees. This study will be covered by a federal Certificate of Confidentiality (CoC) protecting participants against disclosure of sensitive information (e.g., drug use). The NIH office that issues the CoC will be advised of changes in the CoC application information. Participating sites will be notified if CoC revision is necessary.

Participant records will be kept confidential by the use of study codes for identifying participants on CRFs, secure and separate storage of any documents that have participant identifiers, and secure computer procedures for entering and transferring electronic data.

18.4 Health Insurance Portability Accountability Act (HIPAA)

Study sites may be required by their institutions to obtain authorization from participants for use of protected health information. The Lead Node will be responsible for communicating with the IRB and obtaining the appropriate HIPAA approvals or waivers to be in regulatory compliance.

18.5 Investigator Assurances

Each IRB that relies on the central IRB must have on record a Federalwide Assurance (FWA) with the HHS Office of Human Research Protection. This sets forth the commitment of the organization (SITE or IRB) to establish appropriate policies and procedures for the protection of human research subjects, with documentation to be sent to NIDA or its designee. Research covered by these regulations cannot proceed in any manner prior to NIDA's receipt of certification that the research has been reviewed and approved by the IRB provided for in the assurance (45 CFR 46.103(b) and (f)). Prior to initiating the study, the principal investigator at each study site will sign a protocol signature page, providing assurances that the study will be performed according to the standards stipulated therein.

18.6 Research Advisory Panel of California

Prior to initiating the study, the sponsor or designee will obtain written approval from the Research Advisory Panel of California (RAP-C) if any selected sites are in California. Any planned research project to be conducted in California requiring the use of a Schedule I or Schedule II Controlled Substance as its main study medication as well as research for the treatment of controlled substance addiction or abuse utilizing any drug, scheduled or not must be submitted to RAP-C for review and approval prior to study start-up. Study approval is based on review of the study protocol, consent form, and other pertinent study documents. Yearly reports will be provided to the RAP-C by the sponsor or designee in order to obtain continuing study approval.

18.7 Financial Disclosure

All investigators will comply with the requirements of 42 CFR Part 50, Subpart F to ensure that the design, conduct, and reporting of the research will not be biased by any conflicting financial interest. It is the responsibility of the investigator and the entire local research team to maintain appropriate disclosure to their individual institution according to their requirements.

18.8 DEA Registration

XR-NTX is not a controlled substance. No DEA registration is required for facilities to receive, prescribe or dispense study drug.

18.9 Drug Accountability

Upon receipt, the investigator, pharmacist, or authorized designee at each site is responsible for taking inventory of the study drug. A record of this inventory must be kept and usage must be documented. Any unused or expired study drug must be accounted for.

18.10 Inclusion of Women and Minorities

Unless specified in the eligibility criteria, the study enrollment is open to any gender, race, or ethnicity. A diverse group of study sites will be involved so that the study can enroll a diverse study population. If difficulties are encountered in recruiting an adequate number of women and/or

minorities, these will be discussed in national conference calls and face-to-face meetings, encouraging such strategies as linkages with medical sites and/or treatment programs that serve a large number of women or minorities or advertising in newspapers or radio stations with a high female or minority audience.

18.11 IND Requirement

Medications to be used in this study will be used in accordance with their approved labeling and therefore there is no plan to submit an IND application.

18.12 Regulatory Files

The regulatory files should contain all required regulatory documents, study-specific documents, and all important communications. Regulatory files will be available at each participating site for inspection and compliance monitoring prior to study initiation, throughout the study, and at study closure.

18.13 Records Retention and Requirements

Research records for all study participants (e.g., case report forms, source documents, signed consent forms, and regulatory files) are to be maintained by the investigator in a secure location for a minimum of 3 years after the study is complete and closed. These records are also to be maintained in compliance with local IRB, state, and federal requirements, whichever is longest. In the case of HIPAA-protected records, this time length is six years. The sponsor and lead investigator must be notified in writing and acknowledgment must be received by the site prior to the destruction or relocation of research records.

18.14 Audits

The sponsor has an obligation to ensure that this trial is conducted according to good research practice guidelines and may perform periodic quality assurance audits for protocol compliance. The Lead Investigator and authorized staff from the National Lead Study Team; the National Institute on Drug Abuse Clinical Trials Network (NIDA CTN, the study sponsor); NIDA's contracted agents, monitors, or auditors; and other agencies such as the Department of Health and Human Services (HHS), the Office for Human Research Protection (OHRP) and the sites' Institutional Review Board may inspect research records for verification of data, compliance with federal guidelines on human participant research, and to assess participant safety.

18.15 Reporting to Sponsor

The site principal investigator agrees to submit accurate, complete, legible and timely reports to the Sponsor, as required. These include, but are not limited to, reports of any changes that significantly affect the conduct or outcome of the trial or increase risk to study participants. Adverse Event and Serious Adverse Event reporting will occur as described in Appendix A - Adverse Event Reporting Definitions and Procedures. At the completion of the trial, the national Lead Investigator will provide a final report to the Sponsor.

18.16 Informed Consent

The informed consent process is a means of providing study information to each prospective participant and allows for an informed decision about participation in the study. All potential candidates for the study will be given a current IRB-approved copy of the Informed Consent Form

to read. Appropriately qualified and trained study personnel will explain all aspects of the study in lay language and answer all of the study candidate's questions. Participants who remain interested after receiving an explanation of the study will be given an informed consent quiz to test his/her understanding of the trial, the purpose and procedures involved, and the voluntary nature of his/her participation. Those who cannot successfully answer the quiz questions will have the study re-explained by research staff with a focus on those aspects they did not understand. Anyone who cannot demonstrate appropriate understanding of the study will be ineligible to participate and will be assisted in finding other treatment resources. Those who demonstrate understanding of the study and voluntarily agree to participate will be asked to sign the Informed Consent Form. Participants will not be administered any assessments or study procedures prior to signing the informed consent form.

For this study, there will be three consents. There will be two consents for the primary study: one for pre-screening and one for trial consent. The pre-screening consent is verbal only while the trial consent is written and must be signed and dated by the participant. A verbal consent (i.e., waiver of written consent) will also be required for the qualitative interview portion of the study. All consents are to be treated equally in terms of regulatory and protocol requirements (e.g., approved by the IRB before site initiation, etc.).

Study sites may use the template approved by the central IRB. A copy of the IRB-approved consents, along with the IRB study approval, must be sent to the Clinical Coordinating Center (CCC) and the Lead Node prior to the site initiation visit and with each subsequent consent revision. The Informed Consent Form must be updated or revised whenever important new safety information is available or whenever the protocol is amended in a way that may affect a study participant's participation in the trial. The site must maintain the original and signed Informed Consent Form for each participant in a locked and secure location that is in compliance with IRB and institutional policies. The consent forms must also be accessible for quality assurance review and regulatory compliance. Every study participant should be given a copy of the signed document to keep for their reference. Individuals who refuse to participate or who withdraw from the study will be treated without prejudice.

